11.3 Important Protocol Deviations

Per PRA processes, protocol deviations data will be entered into the CTMS, in accordance with the Protocol Deviation Guidance Document. The study team and the sponsor will conduct on-going reviews of the deviation data from CTMS, without regard to treatment assignment in accordance with the Blinding Plan. The per protocol analysis sets determined by types of important protocol deviation must be finalized at the data review meeting (or earlier), prior to database lock.

Based on the protocol deviations data entered into CTMS, the important protocol deviations thought to potentially impact the statistical analyses or subject safety will be listed and tabulated using incidence and percentages by deviation type and randomized treatment group in the FAS. Important protocol deviations are defined in the Protocol Deviation Guidance document. The last approved version of Protocol Deviation Guidance before the database lock will define the per protocol analysis sets.

1) Immunogenicity-Interfering Important Protocol Deviations (IIIPD)

Important Protocol Deviations are subdivided into those that are thought to interfere with immunogenicity and those that do not. These immunogenicity-interfering important protocol deviations (IIIPD) are listed explicitly in Appendix 4 and will be used to identify those subjects that are excluded from the Per Protocol Analysis Set 2 (See Section 8.3). This study population will be used in a sensitivity analysis defined in Section 11.6.1.3.

2) Efficacy-Interfering Important Protocol Deviations (EIIPD)

Important Protocol Deviations are classified into those that are thought to interfere with HbA1c and those that do not. These efficacy-interfering important protocol deviations (EIIPD) are listed explicitly in

Sponsor: Gan & Lee Pharmaceuticals, USA Corporation
Protocol no: GL-GLAT2-3002

Statistical Analysis Plan
Version Date: 16-Nov-2020

Appendix 4 and will be used to identify those subjects that are excluded from the Per Protocol Analysis Set 3 (See Section 8.3). This study population will be used in a sensitivity analysis defined in Section 11.7.1.3.

3) Eligibility-Related Important Protocol Deviations (ERIPD)

Eligibility-related important protocol deviations are important protocol deviations violating any inclusion or exclusion criteria (refer to Appendix 4 for details). This indication will be used in sensitivity analyses for immunogenicity, efficacy, and safety measures to evaluate the impact of these important deviations.

11.4 Demographic and Baseline Characteristics

Demographic information and baseline characteristics will be summarized for the FAS, SS, and PPS. Descriptive statistics will be provided for age, age group, sex, race, ethnicity, baseline body weight, height, BMI, duration of diabetes, baseline HbA1c, baseline immunogenicity result, and presence/absence of thyroid disease (plus a breakdown of type for subjects with thyroid disease, e.g. hypothyroidism, hyperthyroidism, structural abnormality, or thyroid cancer). A listing will be provided for FAS. Additionally, demographic information and baseline characteristics will be summarized by treatment group and disposition status in the SS.

Medical history conditions will be coded using MedDRA version 22.0. The number and percentage of subjects with each medical history term will be summarized by the MedDRA system organ class (SOC) and preferred term using the FAS.

11.5 Treatments

11.5.1 Prior and Concomitant Medications

Medications received prior and concomitantly with IP, categorized according to WHODRUG (Version 2017SEP DDE+HD [Herbal + Enhanced] B3), will be summarized separately using the FAS. The number and percentage of subjects using each medication will be displayed by WHODRUG defined preferred terms.

A separate summary of concomitant OAM will be presented. Additionally, "Insulins and Analogues" selected by WHODRUG ATC level 3 of "A10A" and categorized by ATC level 4 will be summarized separately for prior and concomitant medications.

11.5.2 Extent of Exposure

For the study IP, summary statistics will be provided for SS for duration of therapy and estimated total cumulative dose and overall subject average daily dose (OSADD; defined in Section 7.1). The number and percentage of subjects who experience at least one overdose (as reported in the Overdose CRF page) as well as the number and percentage of those with double average daily dose at any time during the study (defined in Section 7.1) will be provided.

A separate overall summary of overdoses will provide the total number of overdoses experienced by all subjects, number and percentage of overdoses related to an adverse event, and number and percentage of overdoses related to a hypoglycemic event as recorded on the Overdose CRF. Additionally, a summary table will provide the number and percentage of subjects with at least one overdose event, number and percentage of subjects experienced overdose that is related to a hypoglycemic event as reported on the Hypoglycemia CRF, and also the number and percentage of subjects with an overdose that is related to an SAE as reported in the Adverse Event CRF page.

Additionally, a correlation plot of the average daily dose versus the change from baseline in HbA1c result at the corresponding visit will be presented for FAS.

Sponsor: Gan & Lee Pharmaceuticals, USA Corporation
Protocol no: GL-GLAT2-3002

Statistical Analysis Plan
Version Date: 16-Nov-2020

The difference between treatment groups in the mean OSADD will be estimated along with the corresponding 90% CI in the FAS using analysis of variance with treatment as the only independent variable in the model and reported with a p-value.

A listing of the lot number(s) for each subject and a listing of unique manufacturing lot numbers will be provided. Drug accountability will be listed.

A manual summary of subjects with one or more defective IP pens will be provided and discussed in the clinical study report based on information collected outside of the clinical database. This manual summary will include subject ID, site, investigator name, product quality issue reported, and site / clinical research associate comments.

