b At screening, prior and concomitant medications will be collected. At every visit (except for visits to apply a CGM sensor) or telephone call, the Investigator or designee will inquire about concomitant medications, including insulin products taken before the first dose of IP.

c Height and body weight will be measured at the screening visit, and at subsequent visits, only body weight will be measured. The BMI will be calculated and recorded whenever the body weight is measured.

d Routine laboratory testing will include a complete blood count, a metabolic chemistry panel with serum lipids, a thyroid stimulating hormone and free thyroxine.

e Women of childbearing potential will have a urine pregnancy test at screening and at each clinic visit.

f At the screening visit and at Weeks 11 and 25, subjects will attend a brief visit to have a CGM sensor applied. This visit should take place between 8 and 10 days before the scheduled visits at Weeks 12 and 26, respectively. Subjects will also be given a Mealtime & Insulin Dose Record to be completed during the 8-day CGM period that they will bring to the next visit.

g At these visits, subjects will be issued a supply of IP sufficient to last until the next clinic visit. They can also obtain more supplies for glucometer testing if needed.

h At Visit 2, the Investigator or designee will instruct the subject on all study procedures including proper IP administration.

i Subjects will bring the Hypoglycemic Events Record to each visit for review.

j Only serious adverse events to be queried.

Note: See [Section 8.5.8](#) for details about insulin and OAM dose optimization.

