### 8.4.1 Inclusion Criteria

Subjects must satisfy all of the following entry criteria before they will be allowed to participate in the study:

1. Male or nonpregnant, nonlactating female subjects between the ages of 18 and 75 years, inclusive
2. Ability to provide written, personally signed, and dated informed consent to participate in the study, in accordance with the ICH GCP Guideline E6 and all applicable regulations, before initiating any study-related procedures
3. Ability to understand and fully comply with all study procedures and restrictions.
4. Subjects with a confirmed diagnosis of type 2 diabetes mellitus who meet one of the following:
  - a. If insulin-naïve, subjects should have been on at least 2 approved OAMs for at least 12 weeks before screening, and the clinician has decided to add insulin therapy
  - b. If already being treated with a basal insulin, subjects should have been treated with insulin for at least 6 months in addition to at least 1 approved OAM, and must not have changed the type or brand of insulin within 6 months prior to screening
5. HbA1c values as follows:
  - a. If insulin-naïve, HbA1c ≤ 11.0%
  - b. If previously on a basal insulin regimen, HbA1c ≥ 7.0% and ≤ 11.0%
6. Body mass index (BMI) ≤ 45 kg/m^2
7. Adherence to a prudent diet and exercise regimen recommended by the medical provider, and willingness to maintain these consistently for the duration of the study

8. Concomitant medications are allowed, provided that no significant dosing changes are anticipated during the study (see the exclusion criteria below and [Appendix 3 \[Section 17.3\]](#) for specific allowed and prohibited concomitant medications); for concomitant thyroid medications, subjects must have been on a stable dosage for 90 days before screening

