### 9.1 Visit 1: Screening: From Day -14 Through Day -1

At the screening visit, subjects will provide informed consent and will be evaluated for eligibility to participate in the study. After the subject signs the ICF, the following information will be collected or procedures performed:

- Eligibility screening
- Adverse events
- Medical history (including diabetes mellitus and thyroid disease history)
- Prior and concomitant medications (including insulin)
- Vital signs, height, body weight, and BMI
- 12-lead ECG
- Physical examination
- Venous blood samples will be collected for the following tests:
  - Routine hematology and chemistry testing including free T4 and TSH (See [Section 10.5](#) for details)
  - FBG test
  - HbA1c
  - AIA (blood should be collected before the subject administers the regular insulin dose)
- Urine samples will be collected for urinalysis and, for women of childbearing potential, a urine pregnancy test
- A capillary blood glucometer, test strips, and other supplies will be issued and the Investigator or designee will provide instruction and conduct training on how to use the glucometer
- The Investigator or designee will apply a CGM sensor and issue an 8-day Mealtime & Insulin Dose Record, and will instruct the subject about the purpose of the CGM, the need to continue performing glucose self-testing with the glucometer, care of the sensor, and how to complete the Mealtime & Insulin Dose Record (subjects will be instructed to bring the record back to their next visit)
- Subjects will also receive a Hypoglycemic Events Record in which they will record information about any hypoglycemic events during their participation in the study
- During the 2-week period between the screening and randomization visits, subjects already taking a basal insulin will have their dose optimized based on fasting glucose results according to [Section 8.5.8](#), and will have their OAM doses adjusted as needed as a result of insulin dose optimization. Subjects not currently on basal insulin therapy will have their OAM dose optimized in preparation for starting basal insulin.

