5.2 Randomization

Subjects will be randomly assigned in a 1:1 ratio to Gan & Lee Insulin Glargine Injection or Lantus® treatment. Subject randomization will use a randomly permuted block design with varying block sizes and without stratification.

Registration and randomization will take place using a centralized Interactive Web Response System (IXRS). At registration, the IXRS will assign a unique subject identification number that will be used on all of that subject's eCRFs and serious adverse event (SAE) report forms.

This is an open-label study, however, to avoid the introduction of operational bias into final study results and to increase the interpretability and reliability of the data, certain roles of the Sponsor and study team will be blinded. Details are provided in the Data Blinding and Documentation of Aggregate Data Dissemination Plan (hereafter referred to as the Blinding Plan).

6. Endpoints and Covariates

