The duration of diabetes is defined as the number of years from the date of original diagnosis of Type 2 Diabetes Mellitus to the date of randomization (presented in full years):

$$(\text{date of randomization} - \text{date of Type 2 diagnosis} + 1) / 365.25$$

If the date of Type 2 Diabetes Mellitus is partially missing, then the following imputation rules will be applied:

- Missing day, but month and year are present: the day will be imputed as the 1st of the month.

Sponsor: Gan & Lee Pharmaceuticals, USA Corporation
 Protocol no: GL-GLAT2-3002

Statistical Analysis Plan
 Version Date: 16-Nov-2020

- Missing day and month but year is present: the day and month will be imputed as July 1 or date of consent, whichever is earlier.
- Date completely missing: no imputation will be done, and diabetes disease duration will also be missing.

9) Dosing Regimen

- Daily (QD): Dosing where the answer to the question "Was the subject compliant with QD dosing since the previous visit?" is Yes on all Average Daily Dose of Study Drug CRF pages.
- Twice daily (BID): Dosing at least once where the answer to the question on the Average Daily Dose of Study Drug CRF page "Was the subject compliant with QD dosing since the previous visit?" is No and "Subject dosed BID on one or more days" is ticked at least once.

10) Double Average Daily Dose

Double Average Daily Dose is defined as having at least double the average daily dose compared to the first average daily dose after randomization at any subsequent average daily dose assessment.

11) Eligibility-Related Important Protocol Deviation (ERIPD)

Eligibility-related important protocol deviations are important protocol deviations coded to the Inclusion Criteria or Exclusion Criteria categories (refer to Appendix 4 for details).

12) End of Treatment visit

The End of Treatment visit (EOT) is defined as the visit Week 26. Any subject who discontinues from treatment before visit Week 26 will have the Visit 9 procedures performed for their EOT visit.

13) Exposure

- Duration of therapy (presented in weeks with one decimal place)

Duration of therapy is defined as (date of last dose – date of first dose + 1)/7.

- Estimated total cumulative dose (presented in U with one decimal place)

The estimated total cumulative dose for a given subject will be calculated using the following formula:

$$\sum_{i=2}^{n_c} (\text{Number of Days between } C_i \text{ and } C_{i-1}) * \text{Average Daily Dose}_i$$

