Overall Subject Average Daily Dose (OSADD) is defined as the average of all non-missing average daily doses recorded throughout the study after randomization (including scheduled and unscheduled assessments). The study diagram shows that the number of Average Daily Dose assessments is scheduled to be collected at seven in-person visits and 5 telephone visits for each subject (See Section 8 of the Protocol).

19) Overdose

Overdose is identified based on investigator discretion, as recorded in the Overdose CRF page. Overdoses are further classified as being related to an adverse event and as being related to a hypoglycemic event in the Overdose CRF page.

Overdose is also identified programmatically as double average daily dose (see above definition), based on information collected in the Exposure CRF page.

Additionally, hypoglycemic events associated with overdose are captured in the Hypoglycemia CRF page.

20) Previous Exposure to Lantus®

Previous Exposure to Lantus® is defined as No Previous Exposure if no Lantus® treatment is documented within 6 months prior to first dose of IP on the prior/concomitant medications CRF page and as Previous Exposure if at least one dose of Lantus® is documented within 6 months prior to first dose of IP (between and including study day -182 and study day -1).

21) Prior and Concomitant Medications

Prior medications are defined as those with a start date prior to the date of randomization and an end date on or before the date of randomization.

Concomitant medications are defined as those ongoing at the date of randomization or with a start date on or after the date of randomization.

22) Study Day

Study Day 1 is defined as the date of first dose of IP. For subjects whose treatment assignment is randomly assigned but not dosed, Study Day 1 is defined as the date of randomization assignment. For dates prior to Study Day 1, the Study Day is calculated as:

$$\text{Study Day} = (\text{Date of Interest/Assessment} - \text{Date of Study Day 1})$$

For dates post Study Day 1,

$$\text{Study Day} = (\text{Date of Interest/Assessment} - \text{Date of Study Day 1} + 1)$$

23) Study Completers

Subjects with non-missing baseline and scheduled visit Week 26 assessment of AIA and who received IP for at least 22 weeks will be used for the analysis.

24) Thyroid Function Abnormality

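### The between-arm comparison of insulin dose (SAP 11.5.2) leaves out baseline weight and prior basal insulin, and averages over all contacts, so its interval is wider than necessary and late dose divergence is diluted

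*SAP*

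**What the plan says.** SAP 11.5.2 (Extent of Exposure) plans one inferential comparison of dose: "The difference between treatment groups in the mean OSADD will be estimated along with the corresponding 90% CI in the FAS using analysis of variance". That model has a single term, treatment, and a p-value accompanies the estimate. The section gives no margin, hypothesis or decision rule.

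The dose variable is defined in SAP 7.1: "Overall Subject Average Daily Dose (OSADD) is defined as the average of all non-missing average daily doses recorded throughout the study after randomization". Doses are scheduled to be recorded at seven clinic visits and five telephone contacts. The variable is not scaled to body weight, and the SAP contains no U/kg or covariate-adjusted dose analysis.

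The candidate covariates are already collected. Protocol Table 1, footnote c, states: "Height and body weight will be measured at the screening visit, and at subsequent visits, only body weight will be measured". Protocol 9.1 records prior medications, insulin included, at screening. The population is mixed by design. Alongside subjects already on basal insulin, Protocol 8.4.1 admits naive ones: "If insulin-naïve, subjects should have been on at least 2 approved OAMs for at least 12 weeks before screening". BMI may be as high as 45 kg/m². SAP 5.2 allocates by a "randomly permuted block design with varying block sizes and without stratification".

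By contrast, the HbA1c model (SAP 11.7.1.1) adjusts for baseline HbA1c, and the hypoglycemia rate model (SAP 11.8.1) adjusts for site.

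**The concern.** Under Protocol 8.5.8 basal dose is adjusted to fasting glucose. A less potent product could therefore reach the same HbA1c at a higher dose, and someone reading the HbA1c result will want to know whether the arms used similar doses. The HbA1c rule carries no dose condition, and the only planned display linking dose to HbA1c is a correlation plot. That leaves the OSADD contrast as the one interval estimate available.

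Two features make it less informative than the data allow. First, weight and insulin history probably explain a material share of the variation in units per day, and all of that share stays in the error term. Second, a mean over the whole study shrinks any difference that emerges late. A late difference is plausible if antibodies affect dose need, and immunogenicity is this trial's primary question.

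**Working it through.** **Plan's own figures.** The documents give no SD, power or margin for OSADD, so there is no dose figure to reproduce. The sample size behind the calculations can be checked on the primary endpoint (Protocol 12.2: 275 per arm, rate 30%, margin 12%, about 85% power). SE = √(2 × 0.30 × 0.70 / 275) = 0.0391. Power = 2Φ(0.12/0.0391 − 1.645) − 1 = 84.6%, which agrees.

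**Step 1: precision.** If covariates explain a share R² of dose variance, the SE is multiplied by √(1 − R²). R² is assumed.

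| R² | √(1 − R²) | SE reduction |
|---|---|---|
| 15% | 0.922 | 7.8% |
| 25% | 0.866 | 13.4% |
| 35% | 0.806 | 19.4% |

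In units, the unadjusted 90% half-width is 1.645 × SD × √(2/275). For assumed SDs of 20, 25, 30 and 40 U it is 2.8, 3.5, 4.2 and 5.6 U. With SD 30 U and R² 30%, it falls from 4.21 to 4.21 × √0.70 = 3.52 U. That gain equals raising 275 per arm to 275/0.70 ≈ 393.

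**Step 2: validity of the planned interval.** A simulation of 4,000 trials used 275 per arm, half on prior insulin with a 20 U effect, weight SD 20 kg at 0.4 U/kg, and residual SD 22 U (R² about 25%; all assumed). Both models were centred on the true difference of zero. Coverage of the 90% CI was 0.900 with treatment only and 0.905 adjusted. The mean half-width fell from 3.57 to 3.09 U.

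**Step 3: size of chance imbalance.** With half the subjects insulin-naive (assumed), the SD of the difference in naive share between arms is √(2 × 0.25/275) = 4.3 percentage points. At 30% or 70% naive it is 3.9 points. With an assumed naive-versus-experienced gap of 15 to 20 U/day, a 1-SD imbalance moves the unadjusted difference by 0.0391 × 15 = 0.6 U up to 0.0426 × 20 = 0.9 U. Against half-widths of 2.8 to 5.6 U, the 50% case (0.64 to 0.85 U) is between 0.64/5.6 = 11% and 0.85/2.8 = 30%.

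**Step 4: dilution of late divergence.** The scheduled contacts are Weeks 2, 4, 6, 8, 10, 12, 14, 16, 18, 20, 22 and 26. Each recorded dose is taken as the level at its contact week, for a subject with all 12 records.

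- The difference grows linearly from Week 0 to d at Week 26: the mean contact week is 158/12 = 13.2, so OSADD shows 13.2/26 = 51% of d.
- The difference is zero to Week 12, then linear to d at Week 26: the weeks beyond 12 sum to 2 + 4 + 6 + 8 + 10 + 14 = 44, so OSADD shows 44/(14 × 12) = 26% of d.

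Early discontinuers contribute early doses only and count as much as completers, which lowers these shares further. SAP 5.1 acknowledges more early discontinuation than expected.

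**The case against.** The strongest reply is that nothing is wrong with the planned analysis. Randomization makes the unadjusted difference unbiased, its CI already allows for chance imbalance, and the simulation shows nominal coverage. This stands. A reader might infer that imbalance in weight or insulin history invalidates the comparison, or could readily mimic or hide a product difference. The documents do not support that, and Step 3 shows a typical shift well inside the interval.

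A reader might also infer that HbA1c equivalence rests on this comparison. It does not. The comparison sits under exposure, dose is not an endpoint, and the HbA1c rule makes no reference to it. Its relevance is an inference from the titrated design.

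The point about blending titration with steady dosing is weaker than it may seem. Subjects on basal insulin are optimized before randomization. Only the others have a defined post-randomization period, of four weeks, so about 2 of 12 contacts fall in it, for one subgroup. What survives is the dilution of late divergence.

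Some information is planned elsewhere. Baseline weight and prior insulins are summarized by arm (SAP 11.4 and 11.5.1), so an imbalance will be visible, and dose doubling is counted (SAP 11.5.2). None of this gives an adjusted dose difference or a late-dose comparison.

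Finally, every magnitude in units, and R² itself, is assumed. That also stands.

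**Conclusion.** The point holds as a precision and interpretation issue. The planned estimate is unbiased and its 90% CI valid, but the CI is wider than it needs to be: about 8% to 19% off the SE for an assumed R² of 15% to 35%. The dilution figures (51% and 26%) need no assumed variance, but they do depend on the assumed shape of divergence and on complete records. No primary or key secondary test is affected. The change is still worth making because it is cheap and this is the only formal dose contrast available when HbA1c is interpreted.

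**What to change.** Before database lock, amend SAP 11.5.2 as follows.

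- Analyse OSADD by ANCOVA with treatment, baseline body weight and a prior-basal-insulin flag (yes/no). Report the adjusted difference with its 90% CI, and keep the treatment-only ANOVA as supportive.
- Define the flag from the prior medication records. The SAP has only a prior-Lantus definition (7.1). State how bolus-only users are classed, because the protocol synopsis admits them while Protocol 8.4.1 mentions basal insulin only.
- Fit the same model to the last recorded on-treatment average daily dose; for early discontinuers this is the last dose before stopping. Because it mixes time points, show the time of that dose by arm.
- Give U/kg/day with baseline weight as a supportive display. Same-visit weight is unsuitable: none is taken at the five telephone contacts that feed OSADD, and post-randomization weight may itself respond to dose.
- State the analysed n. The FAS includes subjects who were never dosed and so have no OSADD.

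The cost is one derived flag and a few extra table rows, with no new data. Protocol 12.3 allows additional analyses in the SAP.
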